1.0 BACKGROUND

Radiofrequency (RF) technology is commonly used in surgery, minimally invasive treatments and aesthetic applications. RF technology is a safe method for non-ablative (A nonwounding device treatment which stimulates collagen growth and tightens underlying skin) treatment because energy can be precisely delivered through the skin to the dermal tissue beneath without damaging the epidermis. The gentle heating of deep dermal tissue induces collagen denaturation, contraction, and subsequent synthesis. The collagen synthesis, in turn, creates a tightening effect that helps to eliminate mild to moderate facial wrinkles and rhytids (A wrinkle, typically a facial wrinkle secondary to muscular contraction patterns in the skin) and is used also for other cosmetic treatments on the body. Radiofrequency surgery is currently used to remove lesions such as moles, warts and skin tags and perform cosmetic surgeries such as, but not limited to; blepharoplasties, abdominoplasties, breast augmentations, face lifts, labiaplasties, and vaginoplasties. It involves the passage of radio waves into the skin to perform the removal or reshaping of a lesion. Different types of electrodes are used depending on the type of lesion (e.g. fine needle, wire loop, scalpel blade etc.).

In this study this family of generators will be tested for:

General surgical procedures such as (but not limited to);

- o Urologic, thoracic, plastic, reconstructive and gynecological
- o Electrosurgical coagulation (hemostasis or coagulating) of tissue
- o Epilation and telangiectasia

Non-ablative/aesthetic treatments such as (but not limited to);

- Facial wrinkles and rhytids
- Heating for the purpose of elevating tissue temperature for selected medical conditions such as temporary relief of pain, muscle spasms, and increase in local circulation
- Temporary reduction in the appearance of cellulite

2.0 DEVICE DESCRIPTION AND SPECIFICATIONS

The TempSure Class II Electrosurgical cutting and coagulation device and accessories used in this study received 510(k) clearance under K171262 on September 22, 2017 for:

- The 10mm, 15mm, and 20mm TempSure Envi handpieces are indicated for non-ablative treatment of mild to moderate facial wrinkles and rhytids.
- The 18mm, 25mm, and 30mm TempSure Envi handpieces provide heating for the purpose of elevating tissue temperature for selected medical conditions such as temporary relief of pain, muscle spasms, and increase in local circulation.
- The Massage device is intended to provide a temporary reduction in the appearance of cellulite.
- Coagulation/Hemostasis: Using the surgical handpieces and accessories, general surgical procedures including urologic, thoracic, plastic, reconstructive, and gynecological procedures where electrosurgical coagulation of tissue is performed.

And received 510(k) clearance under K182365 on October 24, 2018 for:

- Cutting: snoring, submucosal palatal shrinkage, traditional uvulopalatoplasty (RAUP), myringotomy with effective hemorrhage control, epistaxis treatment, turbinate shrinkage, skin incisions, biopsy, cysts, abscesses, tumors, cosmetic repairs, development of skin flaps, skin tags and blepharoplasty.

- Blended Cutting and Coagulation: snoring, submucosal palatal shrinkage, traditional uvulopalatoplasty (RAUP), myringotomy with effective hemorrhage control, epistaxis treatment, turbinate shrinkage, skin tags, papilloma keloids, keratosis, verrucae, basal cell carcinoma, nevi, fistulas, epithelidma, cosmetic repairs, cysts, abscesses, and development of skin flaps.
- Fulguration: basal cell carcinoma, papilloma, cyst destruction, tumors, verrucae, hemostasis.
- Bipolar: pinpoint precise coagulation, pinpoint hemostasis in any field (wet or dry). Snoring, submucosal palatal, shrinkage, traditional uvulopalatoplasty (RAUP), myringotomy with effective hemorrhage control, epistaxis treatment and turbinate shrinkage

The 60mm handpieces and flexible applicators used in this study are considered investigational in use because they have not been cleared by the FDA.

The Pellevé has been cleared (510(k) K123366) by the U.S. Food and Drug Administration (the FDA) for:

- Non-ablative treatment of mild to moderate facial wrinkles and rhytids for skin phototypes I-IV
- Cutting: snoring, submucosal palatal shrinkage, traditional uvulopalatoplasty (RAUP), myringotomy with effective hemorrhage control, epistaxis treatment, turbinate shrinkage, skin incisions, biopsy, cysts, abscesses, tumors, cosmetic repairs, development of skin flaps, skin tags and blepharoplasty.
- Blended Cutting and Coagulation: snoring, submucosal palatal shrinkage, traditional uvulopalatoplasty (RAUP), myringotomy with effective hemorrhage control, epistaxis treatment, turbinate shrinkage, skin tags, papilloma keloids, keratosis, verrucae, basal cell carcinoma, nevi, fistulas, epithelidma, cosmetic repairs, cysts, abscesses, and development of skin flaps.
- Hemostasis: control of bleeding, epilation, telangiectasia.
- Fulguration: basal cell carcinoma, papilloma, cyst destruction, tumors, verrucae, hemostasis.
- Bipolar: pinpoint precise coagulation, pinpoint hemostasis in any field (wet or dry), snoring, submucosal palatal shrinkage, traditional uvulopalatoplasty (RAUP), myringotomy with effective hemorrhage control, epistaxis treatment and turbinate shrinkage.

And under K132665 for indicated for non-ablative treatment of mild to moderate facial wrinkles and rhytids.

The devices used in this study may be considered investigational because they may not be used within the currently cleared indications for use.

The generators used in this study have multiple modes of operation and a selection of electrode tips and handpieces, the user can easily configure the system for a wide array of applications.

This device study does not meet the FDA definition for a Significant Risk Device study per 21 CFR 812.3(m). The sponsor determines that this is a non-significant risk device study.

Significant risk device means an investigational device that:

- (1) Is intended as an implant and presents a potential for serious risk to the health, safety, or welfare of a subject;
- (2) Is purported or represented to be for a use in supporting or sustaining human life and presents a potential for serious risk to the health, safety, or welfare of a subject;
- (3) Is for a use of substantial importance in diagnosing, curing, mitigating, or treating disease, or otherwise preventing impairment of human health and presents a potential for serious risk to the health, safety, or welfare of a subject; or
- (4) Otherwise presents a potential for serious risk to the health, safety, or welfare of a subject.

The Specifications for The Devices Are:

Surgical Connector	One bipolar and two monopolar surgical handpiece ports		
Neutral Connector	One universal neutral connector compatible with Cynosure neutral electrodes		
Smart Handpiece Connectors	One 4-pin circular connector for both RF energy delivery and temperature sensing (monopolar)		
Modes of Operation	The user can select between different modes of operation.		
Maximum Power	TempSure Handpiece		
	60mm, Flexible Applicator		
	300 Watts (+/- 20%)		
	25mm, 30mm		
	165 Watts (+/- 20%)		
	10mm, 15mm, 20mm		
	120 Watts (+/- 20%)		
	Surgical	Cut	300 Watts (+/- 20%)
		Coag	120 Watts (+/- 20%)
		Blend	300 Watts (+/- 20%)
		Bipolar	40 Watts (+/- 20%)
	Pellevé Mode/Character		
	Cut		
120 Watts			
Coag			
60 Watts			
Blend			
90 Watts			
Fulgurate			
45 Watts			
Bipolar			
120 Watts			

3.0 INTENDED USE

The radiofrequency device used in this study is intended for tissue heating, coagulation, and cutting.

4.0 PROTOCOL

4.1 Purpose and Objectives

The purpose of this study is to develop parameters and assess the safety of the radiofrequency device for a variety of treatments. Treatment results may also be evaluated.

The Primary Objectives are:

- To develop treatment parameters.
- Assess the safety through recording of side effects during course of study.

The Secondary Objectives are:

- Subject satisfaction via continuous verbal feedback during the procedure and at follow up visits.
- Assess the ease of use, patient response, treatment time, functions of the new device.

4.2 Protocol Summary

Subjects are to be enrolled in this clinical study if they are 18 years of age or older. Up to 225 subjects will be enrolled at 8 study centers. All subjects may receive up to 10 treatments or multiple treatment areas. Subjects will receive a phone call or attend a visit at 2 days and/or 1 week post treatment to record side effects. If a side effect is tracked, the site will continue to call the subject until the event resolves. If deemed necessary by the investigator, the subject may attend an unscheduled visit for side effect assessment. The subject may return for optional follow up visits at 30, 90 and 180 days post last treatment for side effect and efficacy assessments.

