4.6 Informed Consent Process and Enrollment

Subjects meeting the subject selection criteria for the study will sign the informed consent form and be assigned a subject identification number. Subjects will be de-identified through their subject identification number, which will be stored in a secure location. Subject identification numbers will be generated chronologically and assigned only to subjects who have met all the study selection criteria and have signed the informed consent form. The informed consent will be obtained prior to a subject's involvement in any study related procedures. Non-English speaking individuals cannot be enrolled in this study. Employees of the sponsor or the Investigator may be enrolled in this study. A subject will be considered enrolled in the study once they have signed the informed consent form.

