4.10 Follow Up

- Subjects will receive a phone call or attend a visit 2 days and/or 1-week post treatment to record side effects. If a side effect is tracked, the site will continue to call the subject until the event resolves. If deemed necessary by the investigator, the subject may attend an unscheduled visit for side effect assessment.
- The subject may return for a follow up visit at 30, 90 and 180 days post last treatment for side effect and efficacy assessments.
- The assessments listed in the schedule of activities and observations table (Section 4.13) will be performed at all follow up visits.
- Adverse events will be assessed at all follow up visits.

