4.11 Unscheduled Visits

An unscheduled visit may be performed at any time during the study at the subject's request or as deemed necessary by the site Investigator. The date and reason for the unscheduled visit will be recorded in the source documentation.

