4.13 Schedule of Activities and Observations

Procedure	Screening/ Pretreatment*	Visit 1-5: Treatment Visits	Visit 6: (optional) 2 Day Post Last Treatment Visit or Phone Call	Visit 7: 1 Week Post Treatment Visit or Phone Call	Visit 8: (optional) 30 Day Post Last Treatment Visit	Visit 9: (optional) 90 Day Post Last Treatment Visit	Visit 10: (optional) 180 Day Post Last Treatment Visit
Medical History	X						
Pregnancy Verification	X						
Informed Consent	X						
Treatment Discomfort/ Pain Evaluation		X					
Treatment		X					
Photographs	X	X	X	X	X	X	X
Subject Experience		X					
User Experience		X					
Diary***		X		X			
OCT***	X	X		X	X	X	
Ultrasound***	X	X		X	X	X	
Subject Satisfaction					X	X	X
Adverse Events Assessment **		X	X	X	X	X	X

* Screening/Pretreatment activities must be performed within 30 days prior to 1st treatment and may be performed on the same day as Visit 1.

** If deemed necessary by the investigator, the subject may attend an unscheduled visit for side effect assessment.

***Ultrasound (US), Optical Coherence Tomography (OCT), and the Diary are optional assessments.

The sponsor anticipates that all subjects can be enrolled within 6 months. The subject participation in this study will last approximately to 1-7 months. The total duration of this study is anticipated to last approximately two years.

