5.0 PREGNANCY

Females may not participate in this study if they are pregnant, breastfeeding, were pregnant within the last three months or are planning a pregnancy during the course of the study.

If the subject thinks they have become pregnant during the study it is important that they inform the Investigator immediately. If she becomes pregnant or thinks that she may be pregnant, she will be removed from the study and will be asked to perform a final evaluation similar to that of the final follow-up visit. The Investigator may request to track the pregnancy and will report the pregnancy to the Sponsor.

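### After the last early contact, new side effects are actively sought and the 6-point satisfaction rating is collected only at optional visits, and the plan does not require the number assessed to be reported

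*Combined protocol and SAP*

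**What the plan says.** Section 4.1 makes safety, judged from side effects recorded while the study runs, a primary objective. Section 4.10 sets the early contact: "Subjects will receive a phone call or attend a visit 2 days and/or 1-week post treatment to record side effects". For the later period, section 4.2 states: "The subject may return for optional follow up visits at 30, 90 and 180 days post last treatment for side effect and efficacy assessments". The schedule in section 4.13 agrees, with a column headed "Visit 8: (optional) 30 Day Post Last Treatment Visit" and the same label on Visits 9 and 10.

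In that schedule the adverse event row is marked at the treatment visits and at Visits 6 to 10. The Subject Satisfaction row, which is the 6-point scale of section 4.14, is marked only at Visits 8 to 10. Satisfaction also has a verbal component, which section 4.1 words as "Subject satisfaction via continuous verbal feedback during the procedure and at follow up visits". A separate subject experience questionnaire is completed at treatment visits.

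Section 16.0 places all subjects who begin treatment in the primary analysis. It summarizes categorical data by counts and percentages without naming a denominator, and leaves the handling of missing values to be chosen later.

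Section 9.0 says that events are captured for the whole study. The section closes by saying that once a subject's study-associated events have resolved, that subject will generate no more adverse event reports.

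**The concern.** A subject who has the early contact and does not come back is not asked again about new side effects. If that subject stays in the primary set and late events are expressed as a percentage of it, the subject counts as event-free without having been assessed. The percentage can then understate the late rate. If the number assessed is not printed, a reader of the report cannot separate no new late events from no question asked. The 6-point rating likewise describes only those who chose to return.

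The closing sentence of section 9.0 makes this worse if a site follows it literally. Section 4.16 expects mild swelling and redness that typically clear within 2 to 24 hours. A subject with such a reaction after the first session could, on that reading, stop generating reports within a day, whatever happened at later sessions or visits.

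**Working it through.** **1. Does any other route reach every treated subject after the last early contact?**

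| Route | Where | Whom it reaches |
|---|---|---|
| Repeat calls: "If a side effect is tracked, the site will continue to call the subject until the event resolves" | 4.2, 4.10 | Only subjects with a side effect already on record |
| Unscheduled visits: "An unscheduled visit may be performed at any time during the study" | 4.11 | Only on the subject's request or the investigator's decision |
| Subject contacts the investigator | 9.0 | Only those who come forward |
| Pregnancy: "she will be removed from the study and will be asked to perform a final evaluation similar to that of the final follow-up visit" | 5.0 | Only subjects who are, or think they may be, pregnant |
| Final visit on withdrawal | 6.0 | Only subjects who withdraw |
| Adverse event check at repeat treatment visits | 4.13 | Later effects of earlier sessions, but nothing after the last session |
| Adverse event check at all visits | 4.10, 4.15 | Only visits that take place |
| Ability to attend all visits as an entry criterion | 4.4 | Does not turn visits labelled optional into required ones |

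None covers a treated subject who completes the early contact and does not return. The statement in section 9.0 that events are captured throughout names no contact that would do so.

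**2. Is the number assessed known?** Sections 4.10 and 4.15 require adverse events to be assessed at every follow-up visit, and the schedule marks them at the same Visits 8 to 10 as satisfaction. The number asked should therefore be recoverable from visit records. Section 16.0 does not require it to be reported. It asks for n only with continuous variables.

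**3. Illustration of size.** There is no figure in the plan to reproduce: it states no return rate, late-event rate or precision target.

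Inputs:
- N = 225, the enrolment ceiling in section 4.2. It is counted at consent, since section 4.6 says "A subject will be considered enrolled in the study once they have signed the informed consent form", so the number treated may be lower.
- Return share f = 1, 0.6 or 0.4. The last two are assumptions.

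With zero events among n assessed, the one-sided 95% upper limit is 1 − 0.05^(1/n).
- n = 225: 1.32%
- n = 0.6 × 225 = 135: 2.19%
- n = 0.4 × 225 = 90: 3.27%

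With five late events (also assumed), the percentage depends on the denominator.
- 5/225 = 2.2%
- 5/135 = 3.7%
- 5/90 = 5.6%

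For satisfaction, if a share p of returners is satisfied, the share among all treated lies between p·f and p·f + (1 − f). The width is 1 − f whatever p is: 40 points at f = 0.6 and 60 points at f = 0.4. This only restates the assumed non-return and is not evidence of its size.

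**4. Sentences that conflict.**
- In section 9.0, capture throughout the study stands against no further reports after resolution. The latter also conflicts with sections 4.10 and 4.15.
- Sections 4.2 and 4.10 allow the 2-day contact, the 1-week contact, or both. The schedule marks the 2-day contact optional and the 1-week contact not. A site could take a 2-day call alone as sufficient under the text but not under the schedule.

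**The case against.** The strongest reply is that this is an open-label, descriptive study meant to develop treatment parameters, and that the optional late visits look deliberate. They are described consistently in sections 4.2, 4.10 and 4.13, and stated participation of about 1 to 7 months suggests that variable follow-up was intended. The most common expected reactions clear within a day, inside the early-contact window. Subjects may have up to 10 treatments, with adverse events checked at each treatment visit, so effects of earlier sessions are sought. No late-event percentage is explicitly planned, and the return shares used above have no source.

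Most of this stands as a limit on weight. It does not close the period after the last session. Section 4.16 also lists scarring, hardness, nodules and loss of hair pigment without saying when they arise, so the documents do not show that all effects of interest fall inside the first week.

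A reader might infer that the number asked about late side effects is lost. The documents do not support that, because the assessment belongs to every follow-up visit attended; what is missing is the requirement to report the number. A reader might also infer that satisfaction as a whole is measured only at optional visits. That is too strong, given the verbal feedback and the experience questionnaire around treatment.

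**Conclusion.** The point holds as a gap in active safety ascertainment after the last early contact, joined to a reporting gap and a contradiction in section 9.0. The missing late contact and the section 9.0 sentence carry the weight. The unnamed denominator alone would be a minor omission.

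Its size cannot be fixed from the documents. The 1.3%, 2.2% and 3.3% limits, the 2.2% to 5.6% spread and the 40- and 60-point widths rest on assumed return shares and, for the spread, on five assumed events. They treat 225 as the number treated and pool all handpieces and treatment areas. It would be wrong to conclude from them that return will be low or that late events are being missed: the documents give neither return rates nor onset times. A plausible intention of the section 9.0 sentence is that a resolved event needs no further updates, but the text does not say so.

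**What to change.** 1. In sections 4.2, 4.10 and 4.13, add one phone contact at 30 days, with the adverse event query and the 6-point satisfaction item, for each treated subject who does not attend Visit 8.
2. In section 16.0, report new adverse events and satisfaction at 30, 90 and 180 days over the number actually assessed, beside the all-treated count. Both are needed: the all-treated figure can understate, and the assessed-only figure can overstate if people with problems are likelier to return. List spontaneous reports from subjects not assessed separately. State that active capture after day 30 is limited to those who return.
3. Reconcile the closing sentence of section 9.0 with its own statement of capture throughout the study and with sections 4.10 and 4.15, so that new events continue to be recorded. Reconcile the early-contact wording in sections 4.2 and 4.10 with the schedule.

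The cost is one short call per Visit 8 non-attender, by the phone route the study already uses, a few table columns, and a formal amendment with written IRB approval under section 20.0. The late-event rate may look less favourable. The call can reach only subjects not yet past day 30. The revision log in Appendix A runs from January 2017 to March 2019 against an expected duration of about two years, so many may already be past it. For them, only items 2 and 3 help. Days 90 and 180 remain dependent on voluntary return and can only be disclosed.

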4.3 Protocol Study Design

This investigation is a multi-center, prospective, open label study.

4.4 Criteria

Subjects will meet the criteria described below.

Inclusion Criteria:

- A healthy male or female 18 years of age or older.
- Understands and accepts obligation not to receive any other procedures on the treatment area through the length of the study.
- Understands and accepts the obligation and is logistically able to be present for all visits.
- Is willing to comply with all requirements of the study and sign the informed consent document.

Exclusion Criteria:

- Is pregnant or of child bearing potential and not using medically effective birth control or has been pregnant in the last 3 months, currently breast feeding or planning a pregnancy during the course of the study.
- The subject has active or localized systemic infections.
- The subject is currently enrolled in an investigational drug or device trial, or has received an investigational drug or been treated with an investigational device within in the area to be treated 6 months prior to entering this study.
- Any other types of cosmetic treatments in the area to be treated in the past 6 months are cautioned and determined at the discretion of the investigator.
- The subject has a history of keloids.
- The subject has evidence of active systemic or local skin disease that may alter wound healing.
- The subject has scarring or wounds in the treatment area that would interfere with study assessments.
- The subject has a metal implant (such as but not limited to; titanium orbit or metal chin repair) in the face or head that would interfere with study treatment, or subject

has an electronic implantable device (such as but not limited to; pacemakers and embedded defibrillators).

- The subject has any condition or is in a situation which in the investigators opinion may put the subject at significant risk, may confound study results or may interfere significantly with the subject's participation.

